### Recruitment

Recruitment data will be summarized in a flow diagram.

### Screening data

Screening data will be summarized for each study group.

### Withdrawal and follow-up

Should reasons for withdrawal be known, these will be described, including the timing of withdrawal.

### Baseline patient characteristics

Demographic data will be summarized by descriptive statistics per dose group and will include the total number of observations (n), plus the mean, standard deviation (SD) and range for normally distributed continuous variables and number and percentages for dichotomous variables. This data will be tabulated. Where applicable, continuous outcomes that are not normally distributed will be transformed using a suitable transformation before reporting means and SDs. Where a suitable transformation cannot be found, the mean and SDs will be substituted with the median and interquartile ranges. For discrete (or count) data we will report the medians and interquartile ranges. Binary data will be presented as counts (n/N) and proportions.

## Analyses in relation to endpoints

### Safety outcome analyses

- For each solicited (local or systemic) adverse event type, the number and proportion of participants experiencing that AE within the Protocol-defined timeframe will be tabulated by severity grade for each dose group and for the entire study population. This will also be tabulated for participants experiencing any solicited local, any solicited systemic and any unsolicited AE. Where applicable, we will compare these proportions between groups.

Relatedness (possibly, probably or definitely) of solicited AEs to TB31F administration may also be presented.

- For each related unsolicited adverse event type (categorized by MedDRA), the number of events per dose group and overall study population will be described and categorized by severity grade and relation to TB31F administration. (Outcome measure 1).
- The proportion of individuals with grade 1, 2 and 3 adverse events may be compared between groups.
- The total number of grade 1, 2 and 3 adverse events as count data may be compared between groups.
- Individual serious adverse events (SAEs) will be summarized, including relatedness to TB31F administration.
- Withdrawals due to AEs/SAEs will be summarized per group.

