## Randomization

Eligible participants will be assigned the next sequentially numbered study ID number based on a pre-printed Study ID List created by an independent statistician. Eligible participants will be randomised within each dose-group to either the control sub-group or the TB31F sub-group using a 1:2 ratio for Cohort 1 and Cohort 2. The randomisation codes will be provided to the study pharmacist. The study pharmacist in Mali will prepare the intervention for the study participants. For cohort 2, randomization will be performed in blocks of varying sizes.

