#### Safety outcome measures:

1. Occurrence of at least possibly related
  - a) solicited local and systemic adverse events (AEs) within 7 days of mAb TB31F administration
  - b) unsolicited AEs within 28 days of mAb TB31F administration
  - c) serious adverse events during the entire study period

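### Unsolicited adverse events by type are described only if judged related and only as event counts, so no specific type is compared between TB31F and saline regardless of relatedness

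*SAP*

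**What the plan says.** Outcome 1 (SAP, Safety outcome measures) opens with "Occurrence of at least possibly related", and its second item is "unsolicited AEs within 28 days of mAb TB31F administration".

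The second bullet of Safety outcome analyses carries the filter into the by-type description: "For each related unsolicited adverse event type (categorized by MedDRA), the number of events per dose group and overall study population will be described". The counts are also split by severity grade and by relation to TB31F.

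The first bullet treats solicited events differently. Each type is tabulated as the number and proportion of participants, whatever the relatedness. It then adds aggregate rows: "This will also be tabulated for participants experiencing any solicited local, any solicited systemic and any unsolicited AE". On comparison it says: "Where applicable, we will compare these proportions between groups".

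The Randomization section says what a dose group holds: "Eligible participants will be randomised within each dose-group to either the control sub-group or the TB31F sub-group using a 1:2 ratio".

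**The concern.** Safety is a primary objective in both cohorts, and the trial has a concurrent saline control. That control allows an excess of a particular event to be seen by comparing randomised arms, without a case-by-case causality judgement. In Cohort 2 every participant is naturally infected with *P. falciparum*, so background illness is to be expected and some of it may well be judged unrelated.

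The by-type description makes little use of the control, for three reasons.

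- An event enters only after a causality judgement.
- It enters as a count, so one participant with several episodes looks the same as several participants with one each.
- No TB31F-versus-saline contrast by type is stated, and the term that defines the columns has more than one meaning in the SAP.

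At stake is whether the main report can show that a specific unsolicited event is more frequent on TB31F.

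**Working it through.** **1. Arm sizes.** From Tables 1 to 3, TB31F is 5 × 10 + 2 × 30 = 110 and saline is 5 × 5 + 2 × 15 = 55. The total of 165 reproduces the SAP's stated minimum. By-type contrasts available are 10 v 5 in each Cohort 1 group, 30 v 15 in each Cohort 2 group, 60 v 30 in Cohort 2 and 110 v 55 overall.

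**2. Where unsolicited events appear in the plan.**

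| Place in SAP | Related only? | By event type? | Unit | Between-group comparison |
|---|---|---|---|---|
| Safety outcome analyses, bullet 1, any unsolicited AE | No | No | Participants | Where applicable |
| Bullet 2 | Yes | Yes | Events | None stated |
| Bullets 3 and 4, AEs by grade | No | No | Individuals; events | Optional |
| SAEs; withdrawals due to AEs | No | Individual SAEs | Summaries | None stated |
| Clinical Laboratory Data Analysis | No | Laboratory only | By participant; per group | None stated |
| Safety reports (Statistical interim analyses) | No | Listing | Events | None |

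No row gives a specific unsolicited event type, regardless of relatedness, as participants, by TB31F and saline.

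**3. Counts under 1:2 allocation.** Take 6 events on TB31F and 6 on saline in one Cohort 2 group, one per participant. The rates are 6/30 = 20% and 6/15 = 40%, so equal counts mean twice the rate on saline. A reader can divide by the group sizes, but that gives events per participant. It does not give the proportion affected, because the same 6 events could come from one person.

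**4. Effect of the relatedness filter.** The SAP gives no event rates, so these are assumptions: Cohort 2 with 60 v 30, an event type in 50% on TB31F and 30% on saline, one event per participant, and the same share f called related in both arms. The analysed rates are 50f and 30f. Power is two-sided at 0.05 by normal approximation, Φ[(d − 1.96·SE₀)/SE₁]. Here d is the difference, SE₀ uses the pooled rate and SE₁ the separate rates.

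| f | Rates | Difference | Risk ratio | SE₀, SE₁ | Power |
|---|---|---|---|---|---|
| 100% | 50% v 30% | 20 points | 1.67 | 0.1108, 0.1057 | about 44% |
| 50% | 25% v 15% | 10 points | 1.67 | 0.0921, 0.0859 | about 17% |
| 25% | 12.5% v 7.5% | 5 points | 1.67 | 0.0695, 0.0643 | about 9% |

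With SE₁ in place of SE₀, the first and last rows become about 47% and 12%.

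**5. What an all-cause contrast could show.** With the same formula and assumed rates:

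| TB31F v saline | 110 v 55 | 30 v 15 |
|---|---|---|
| 20% v 5% | about 76% | about 22% |
| 25% v 10% | about 64% | about 19% |
| 30% v 10% | about 86% | about 29% |

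A single group has little power, but all TB31F against all saline is informative. These figures ignore differences between doses and cohorts.

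**6. Meaning of *dose group*.**

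- Randomization: it holds a control and a TB31F sub-group.
- Tables 1 to 3: control is a separate row in the Dose column.
- Pharmacokinetic analysis approach: per-dose-group results are for TB31F recipients.
- Trial population: read literally, the primary safety data include only those who receive TB31F, so saline recipients are left out.

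These cannot all govern the safety tables.

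**The case against.** The strongest reply is that unrelated events are still reported. The safety reports, including the one at study completion, list all adverse events. The any-unsolicited row, the grade comparisons, the SAE and withdrawal summaries and the laboratory section have no relatedness filter. This stands: a reader might infer that unrelated events are dropped, and the SAP does not support that. What it lacks is the by-type table. The laboratory section also means that anaemia or raised liver enzymes are poor examples of lost events, and the SAP does not list which symptoms are solicited.

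A second reply is that the filter does not bias the effect. If it acts equally in both arms, the risk ratio is unchanged, so a claim of bias towards no effect goes too far. The loss is in absolute difference and precision.

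A third concerns pooling. A reader might infer from Randomization that the by-type table mixes TB31F and saline in each column. Under that reading, 9 events in a Cohort 2 group of 45 could be 9/30 v 0/15 (Fisher p = 0.020), 6/30 v 3/15 (p = 1.0) or 4/30 v 5/15 (p = 0.14), and the table would print 9 each time. The other uses of the term do not bear that reading out, so pooling is possible but not established. Only the ambiguity is.

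Finally, Outcome Definitions refers to Protocol section 2, which is not at hand. The related-event outcome may be fixed there, which is a reason to add to it and not to replace it.

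**Conclusion.** The point holds for unsolicited events by type. They are described only when judged related and only as event counts, and no TB31F-versus-saline comparison of any specific unsolicited type regardless of relatedness is planned. It does not extend to the whole safety comparison: solicited types and the any-unsolicited row are tabulated by participant and may be compared.

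On the assumed rates, with a quarter of events called related, a 20-point difference becomes 5 points and power falls from about 44% to 9%, at a constant risk ratio of 1.67. The size depends wholly on the assumed rates, on the share called related, and on that share being equal in both arms. The missing table does not depend on any of these. The inconsistent use of *dose group* and the wording of the safety population are a separate matter to reconcile. The change should be made; the data are already being collected.

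**What to change.** 1. Keep outcome 1 and its related-event description as defined.
2. Add to Safety outcome analyses a table of all unsolicited adverse events by MedDRA term, regardless of relatedness. Give participants with at least one event (n/N, %) first and event counts second, with related events as a subset.
3. Use a column for each TB31F sub-group and one for its concurrent saline sub-group, plus all TB31F (N = 110 at the planned minimum) and all saline (N = 55).
4. Define *dose group* once and use it consistently in Randomization, the design tables, the pharmacokinetic section and the safety section. Reword Trial population so that saline recipients are included in the primary safety data and shown separately.

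The cost is SAP wording and longer tables from data already collected. Listed event rates will look higher because background illness is included.

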### Clinical Laboratory Data Analysis

- All clinically significant laboratory abnormalities will be analyzed by participant and will include details of onset time, duration, severity and relationship to the study dose.
- Any clinically significant deviations in routine laboratory test results, as determined by the investigator, will be summarized per group.
- Isolated laboratory abnormalities will be reported as unsolicited AEs if they are considered clinically relevant by the investigator.

### Pharmacokinetic outcome measures

PK measures are dependent on quantification of TB31F antibody levels by ELISA. The ELISA will be conducted in Mali and/or the Netherlands. For this, serum samples are collected at the following time-points:

	0	1	5	7	14	21	28	42	56	84
Safety cohorts*	X	X	X	X	X	X	X	X	X	X
Efficacy cohorts	X	X	X		X		X		X	X

\*safety cohort group 1 only has follow-up until day 28; safety cohort groups 2-5 have follow-up until day 84.

### Analysis approach:

- For all ELISA samples, TB31F antibody density and prevalence will be determined by ELISA. All samples will be processed in duplicate alongside blank wells (for background correction), a standard curve (for concentration interpolation), and non-treated local controls (for seropositivity calculation). Optical density values from duplicate observations will be compared using the coefficient of variation (CV) and will be re-run if the CV exceeds 30%. OD values in agreement will be converted to concentrations using ADAMSEL software based on plate specific control wells; the mean of duplicate concentration estimates will be used for analyses. Antibody density will be expressed in  $\mu\text{g/mL}$ .
- Seropositivity will be calculated using either a) the pooled concentration values of non-treated local controls (including trial specific controls), defined as the mean of these values plus 2 standard deviations, or b) using a two-normal compartmental mixture model, using all values from the control and treated samples, in which the mean of the lower normally distributed population of values plus 2 SD defines the threshold for positivity.

- TB31F antibody density will be plotted over time per individual and either as a mean or geometric mean per group. Mixed effects models may be used to investigate the interaction of timepoints and group on TB31F antibody concentration, allowing for participant specific random intercepts to control for the correlation within individuals.
- TB31F pharmacokinetics will be analyzed using standard non-compartmental methods to establish the maximum concentration ( $C_{max}$ ), terminal half-life ( $t_{1/2}$ ), area under the curve (AUC  $0-\infty$ ) and Volume of Distribution ( $V_d$ ) for each participant who received mAb TB31F. Additionally, the absorption rate constant ( $K_a$ ) will be determined. Geometric mean and geometric coefficients of variation of  $T_{1/2}$  and  $V_d$ , as well as of dose-adjusted  $C_{max}$  and AUC will be reported per dose group and overall.

### Efficacy outcome measures

#### **Efficacy outcome measures related to within-group % reduction in proportion infected mosquitoes:**

We will determine averaged within-individual percent reduction in the proportion of mosquitoes infected at days post-treatment (1, 5, 14) compared to baseline (day 0) for each group. This will be assessed through DMFA and DSF and outcomes for these different feeding assays will be presented separately as percentage reduction (with 100% as total reduction of transmission, and negative values as enhanced transmission) with 95% confidence interval. Data will be analysed for all individuals who received the product per protocol and only for those individuals who are infectious at baseline (i.e. infecting at least one mosquito with any number of oocysts). All analyses on within-individual percentage reduction in the proportion of infected mosquitoes will use a mixed effects generalized linear model assuming a binomial error structure and a log-link, using individual mosquito data with day of follow-up and dose of TB31F and their interaction as fixed effects. A random intercept will be added to models to allow for participant-level variation in pre-intervention transmissibility and thus account for the correlation between outcomes for mosquito samples from the same participant (i.e. intra-cluster correlation).

In exploratory analyses, these analyses will be performed following stratification for naturally acquired transmission reducing immunity, as quantified by SMFA at baseline (pre-TB31F administration) samples.

The impact of naturally acquired transmission reducing immunity, assessed in baseline samples by SMFA (TRA>50%; TRA>80%) and by antibody prevalence to known gamete antigens Pfs230 and Pfs48/45, on infecting mosquitoes will also be determined. For this, TRA as categorical variable and antibody prevalence (binary variable), will be added as fixed effects to mixed effects logistic regression models on proportion infected mosquitoes at baseline (pre-TB31F administration). These models may be expanded to include human genetic factors (e.g. a fixed effect for HbAS or HbAC carriage as compared to wild-type HbAA).

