## Sample size

The sample size is standard for the safety cohorts without formal sample size estimation. Sample size is informed by the anticipated efficacy from an earlier Phase I study and the transmission blocking effects observed in similar Malian cohorts when treated with transmission blocking drugs; this is done for the efficacy cohort only. This sample size for the efficacy cohort (n=30 per group) will give us 97% empirical power to detect >80% reduction in infectivity (defined as the percentage of mosquitoes with at least one oocyst) with a one-tailed test with a 0.025 level of significance when dissecting at least 40 mosquitos per participant at each timepoint. This power calculation is based on an online tool based on mixed effects logistic regression, an expected reduction in infectivity of 90%, an expected baseline proportion of infectivity of 15% for the average participant (accounting for non-infectious participants), and a conservative expected intra-cluster correlation of 0.5. Of note, this includes non-infectious individuals. In the four years that we performed NECTAR studies with a highly similar

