study population, 66.0-79.5% of individuals infected at least one mosquito at enrolment with 14.2-17.0% of mosquitoes becoming infected. The power calculation given above includes all individuals (infectious and non-infectious). If we retain 30 individuals per arm and exclude those individuals who are not infectious at baseline ( $\leq 10$ ), the expected percentage of infected mosquitoes will increase from 15% (in the situation where some individuals infect no mosquitoes) to  $\sim 20\%$ . Based on a mixed effects logistic regression we looked at 200 simulations with an expected reduction in infectivity of 90%, an expected baseline proportion of infectivity of 20% for the average participant, and an expected intra-cluster correlation of 0.4. We estimated 91.5% empirical power to detect  $>80\%$  reduction in infectivity with a one-tailed test with a 0.025 level of significance when including 30 participants (of whom 20 are included in the analysis, i.e. after excluding non-infectious individuals) and dissecting 40 mosquitoes per participant at each timepoint. Importantly, these analyses are based on DMFA where venous blood is offered to mosquitoes. We and others have previously demonstrated that mosquito infection rates are at least 2-fold higher when allowing mosquitoes to feed directly on the skin of participants. When the expected baseline proportion infected mosquitoes is updated to account for higher infection rates by skin feeding (30% for the average participant) and we conservatively increase intra-cluster correlation to 0.8, we estimated 96% empirical power to detect  $>80\%$  reduction in infectivity with a one-tailed test with a 0.025 level of significance when including 30 participants and dissecting 40 mosquitoes per participant.

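### The log-link model for the percent reduction has only a participant intercept, so under the SAP's own logistic planning model its 95% interval is too narrow and the >80% decision is miscalibrated

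*SAP*

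**What the plan says.** The analysis section on within-group % reduction in the proportion of infected mosquitoes prescribes a "mixed effects generalized linear model assuming a binomial error structure and a log-link". It is fitted to individual mosquitoes, with day, dose and their interaction as fixed effects. The only random effect is the participant's: "A random intercept will be added to models to allow for participant-level variation in pre-intervention transmissibility". The section says that this accounts for correlation between mosquitoes from one participant, and it promises a percentage reduction with a 95% confidence interval. It names no participant-by-day term, random slope, robust variance or bootstrap.

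Outcome 8 is the group average of the within-individual reduction at day 5 against day 0, by DMFA.

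The Sample size section uses another model: "This power calculation is based on an online tool based on mixed effects logistic regression". It assumes "an expected baseline proportion of infectivity of 15% for the average participant", a 90% reduction and an ICC of 0.5, and concludes: "This sample size for the efficacy cohort (n=30 per group) will give us 97% empirical power to detect >80% reduction in infectivity". The test is specified "with a one-tailed test with a 0.025 level of significance when dissecting at least 40 mosquitos per participant at each timepoint". A second calculation (baseline 20%, ICC 0.4, 20 analysed participants) is also logistic: "Based on a mixed effects logistic regression we looked at 200 simulations".

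**The concern.** A participant intercept absorbs differences in overall infectivity. It does not absorb differences between participants in the day-5/day-0 ratio, and any such differences are left out of the standard error.

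The SAP's own planning model implies that they exist. A constant odds ratio combined with a wide spread of baseline infectivity gives each participant a different risk ratio. The analysis model is therefore misspecified under the assumptions used to size the trial. With that spread, a log link also allows fitted probabilities above 1.

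At stake are the interval around the first-listed efficacy outcome, any statement about >80% based on it, and whether the stated power applies to the planned analysis.

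**Working it through.** **Inputs (SAP, Sample size).** n = 30; 40 mosquitoes per feed; baseline 15%; reduction 90%; ICC 0.5; one-sided 0.025. Assumptions of mine: the ICC is on the latent logit scale, and the 90% refers to the average participant.

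**1. Reproduce the stated power.** Random-intercept SD = √[ICC/(1−ICC) × π²/3] = √3.290 = 1.81. Simulating paired day-0 and day-5 counts, fitting the logistic random-intercept model and testing the average participant's reduction against 80% gives 97.5% (stated 97%). The second scenario (SD 1.48, n = 20) gives 93.0% (stated 91.5%). The skin-feeding scenario (ICC 0.8, stated 96%) is matched only roughly: 98.5% on the odds-ratio scale, 72% on the risk-ratio scale.

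**2. Risk ratios implied by the planning model.** logit(0.15) = −1.735 and logit(0.015) = −4.184, so the log odds ratio is −2.450 (odds ratio 0.086). For a participant u SDs from average, p0 = expit(−1.735 + 1.81u) and p5 = expit(−4.184 + 1.81u):

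| u | p0 | p5 | p5/p0 | reduction |
|---|---|---|---|---|
| −1 | 2.8% | 0.25% | 0.089 | 91% |
| 0 | 15% | 1.5% | 0.100 | 90% |
| +1 | 52% | 8.5% | 0.164 | 84% |
| +2 | 87% | 36% | 0.419 | 58% |

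The log-link model treats the fourth column as one constant.

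**3. Three different reductions.** Integrating the same model over u gives 90.0% for the average participant, 86.8% for the averaged within-individual reduction (the mean of 1 − p5/p0), and 79.3% for the ratio of group means (1 − mean p5 / mean p0).

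**4. Interval width.** Log-link random-intercept model fitted by maximum likelihood to data from the planning model:

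- Baseline 15% for the average participant: SD of the log ratio 0.249 against mean SE 0.143 in one set of runs (ratio about 1.75, coverage 74%), and 0.27 against 0.15 in another (1.8, about 74%).
- Baseline 15% as the group mean: 0.31 against 0.19 (1.6), coverage about 77 to 78%.
- ICC 0.4, n = 20: ratio 1.63 to 1.70, coverage 76 to 79%.
- All three doses and four days in one model (160 trials): ratio 2.1 to 2.3, coverage about 64%.
- ICC 0.5 read as a variance of 0.5: ratio 1.06 to 1.07, coverage 92 to 93%.

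Coverage here is of the model's own target. Monte Carlo error is about 1 to 1.5 points (about 3 for the full model). Fitted probabilities above 1 had to be capped; a further check of 400 trials per setting, capped at 0.999, gave coverage of 68 to 74%.

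**5. Calibration of the >80% decision.** Claim made when the upper 95% limit of the risk ratio is below 0.20; latent ICC 0.5, n = 30:

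- Ratio of group means exactly 0.20: claimed in about 10 to 23% of trials (nominal 2.5%). One set of runs with a group-mean baseline gave 6 to 7%.
- Averaged within-individual reduction exactly 80%: claimed in about 0.3%, because the log-link model then estimates about 71%.
- Average participant's reduction exactly 80%: claimed in 0.0%.
- Planned 90% reduction for the average participant: claimed in about 12 to 16%, against the stated 97%. The log-link estimate averages about 81% there, because highly infectious participants supply most infected mosquitoes and have the smallest reductions.

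**The case against.** **A reader might infer that >80% would be claimed falsely too often.** The SAP does not support this as a general statement. Inflation appears when the target is the ratio of group means, whereas outcome 8 is a within-individual average. With a group-mean baseline of 15% (intercept −2.60, SD 1.81, odds ratio 0.107), a group-mean ratio of 0.20 corresponds to an averaged within-individual reduction of 86.6%. Claims of >80% are then true for the SAP's endpoint. With that endpoint set to exactly 80%, the error runs the other way. An inflated rate for it (14.6%) appeared only at ICC 0.8, where the fits depend on the probability cap.

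**Heterogeneity beyond the planning model has no figure in the SAP.** With assumed between-participant SDs of 0, 0.3, 0.5 and 1.0 in the log risk ratio, coverage is 94.5%, 91.8%, 85.2% and 67.0%. This is a range of assumptions, and the conclusion does not rest on it.

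**The ICC scale is not stated.** This stands as a limit. The latent reading is preferred because it reproduces 97%; the variance reading makes the interval problem small.

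**No >80% rule appears in the analysis section.** True: the test is given only under Sample size. The interval would still be read against that margin, and its width is wrong whether or not a formal test is made.

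**Permutation tests are planned.** The Multiple comparisons section recalculates p-values. It leaves the confidence interval unchanged and describes no permutation test against an 80% margin.

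**Conclusion.** The concern holds as a mismatch between planning and analysis. With the ICC on the latent scale, the log-link random-intercept model understates the standard error by a factor of about 1.6 to 1.8, and its 95% interval covers its own target in about 74 to 78% of trials. This holds whether 15% is the average participant's baseline or the group mean. Under the variance reading of the ICC, coverage is 92 to 93%.

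The >80% decision is not calibrated, but no single direction of error can be asserted: it is too liberal for a ratio of group means and far too conservative for the SAP's within-individual endpoint. For the planned effect, the stated 97% power belongs to the logistic analysis; the specified log-link analysis gives about 12 to 16%.

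**What to change.** Before unblinding, amend the SAP to:

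1. State which reduction is the target. Keep the averaged within-individual reduction of outcome 8 unless it is deliberately changed; a ratio of group means must not replace it by default.
2. Use the same logit mixed model for planning and analysis, with a participant intercept and a participant-by-day random effect.
3. Derive the percent reduction for that target from the fitted model, with a 95% interval from a participant-level bootstrap or equivalent. A sandwich standard error on the log-link model is not enough: at n = 30 it gave 90% coverage and 8.5% claims at a group-mean ratio of 0.20.
4. State the ICC scale and restate the power for this analysis.

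In simulation under the planning model, the logit model with the participant-by-day term gave 96% coverage and 1.3% false claims for the ratio of averaged proportions. The same check should be run for the within-individual target before the method is fixed.

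The cost is new SAP wording, a changed link and interval method, and some added analysis work. Intervals will be wider, and the stated power will probably fall.
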